According to the Centers for Disease Control and Prevention, the number one cause of death and morbidity among children ages 1-19 is unintentional injury. Each year, approximately 12,000 children die from unintentional injury causes (1). Of all injury causes, motor vehicle crash leads to the most number of deaths to children in U.S. as passengers, teen drivers and pedestrians. Almost 400,000 injured teen drivers and occupants were seen in emergency departments in the US in 2005 (2). In the U.S., falls lead to the highest number of childhood injury emergency department visits followed by injuries due to being struck by or against an object (1). Fire or burns are also an important cause of injury as the second leading cause of injury death to children between 1 and 19 (1).

Unintentional injuries, particularly severe injuries that impact daily functioning, can have longlasting psychological effects. Prevalence of posttraumatic stress symptoms is estimated at 29% during the first month post-trauma and 13% between 3-6 months post-trauma. (3)

Within 12 months of being hospitalized because of injury, 19-32% of adolescents developed PTSD. (4) A variety of injury experiences can lead to PTSD symptoms including traffic crashes, burns, falls and animal attacks. (5) Adolescents involved in a mass burn incident had significantly more mental problems than community controls one year after the incident (6), and, 12% of schoolchildren exposed to an industrial fire met the criteria for PTSD. (7) Approximately 30% of pediatric pedestrian injury cases have acute stress disorder or PTSD. (8-10) Many cases of psychological trauma are missed in hospital settings and sent home. This proposed project will empower families with skills to identify trauma-induced mental health distress and resources for referral to advanced mental health care.

Our innovative project addresses the need for evidence-based practices to improve the acute care of children post-injury. Psychological First Aid (PFA), analogous to physical first aid (11), “uses interpersonal skills provided by individuals to respond to psychological consequences of [trauma] in their own lives, as well as in the lives of their family, friends, and neighbors (p. 4–5)” (11). Informed by previous research on posttraumatic risk and resilience, PFA provides information, education, comfort and support through human contact in order to accelerate recovery and promotion of mental health (12, 13).

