The focus group data and key informant interviews will be analyzed using content analysis and identification of themes. Focus group and interview data will also be used to incorporate changes into the LPC for Injured Kids program.

Phase 2

If we achieve randomization, we will compare the differences in distributions between intervention and control groups using simple chi-square tests for categorical outcomes (low, medium, high levels of coing; being symptomatic for PTSD, Depression, etc.) and t-tests or Wilcoxon rank-sum tests for continuous variables depending on their normality (e.g. scores for PTSD, depression, social support).

If we do not achieve randomization (i.e. distribution of demographics are not balanced across intervention and control arms), we will also adjust for confounding using Generalized Linear Models and appropriate link functions (logit for binary outcomes, linear for continuous outcomes).

XI.2 *Provide the rationale or power analysis to support the number of subjects proposed to complete this study.***Phase 1**

The research team needs each final focus group to contain at least 6 parents or providers to get an adequate response to the focus group questions. The focus group will have potentially unpredictable schedule, either due to children in the home (parents) or heavy work load (providers) therefore we are recruiting 10 members per focus group to ensure we have at least 6 attending each focus group.

Phase 2

We conducted sample size based on testing a moderate effect size of 0.5 standard deviation comparing Trauma Education vs Link. With an alpha of 0.05, a sample size of 134 parent-child dyads in each of the arms (n=268) has 100% power to examine comparisons. We will oversample by 12% for a total n = 300.

XII. Future Research

XII.1 *Do you wish to keep any information about subjects involved with this research project so that members of the current research team may contact them in the future for your own research projects?*

No

XII.2 *Do you wish to keep any information about subjects involved with this research project so that [other researchers](#) may contact them for future research?*

No

XII.4 *Does this project involve storing any data, tissues or specimens for future research?*

No

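### The 100% power in XI.2 is slightly overstated (about 98% for 0.5 SD) and too broad, because an effect in SD units covers only the continuous scores and not the categorical outcomes in XI.1

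*Protocol*

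**What the plan says.** Protocol XI.2 (Phase 2) names one effect: "We conducted sample size based on testing a moderate effect size of 0.5 standard deviation comparing Trauma Education vs Link". The next sentence gives the result: "With an alpha of 0.05, a sample size of 134 parent-child dyads in each of the arms (n=268) has 100% power to examine comparisons". It then adds 12% to reach 300 in total. Whether alpha is one- or two-sided is not stated. Allocation is 1:1 (VII.E.2).

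Protocol XI.1 (Phase 2) plans two kinds of test. For categorical outcomes it lists "simple chi-square tests for categorical outcomes (low, medium, high levels of coing; being symptomatic for PTSD, Depression, etc". For continuous outcomes it lists "t-tests or Wilcoxon rank-sum tests for continuous variables depending on their normality (e.g. scores for PTSD, depression, social support". If the arms turn out unbalanced, it adds generalized linear models with links described as "logit for binary outcomes, linear for continuous outcomes".

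XI.2 gives no comparator rate, difference in proportions or odds ratio. Section 1.6 does give background rates, which XI.2 does not use: "Prevalence of posttraumatic stress symptoms is estimated at 29% during the first month post-trauma and 13% between 3-6 months post-trauma", and "Within 12 months of being hospitalized because of injury, 19-32% of adolescents developed PTSD".

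**The concern.** Two things look wrong. First, power of exactly 100% is not attainable, so the figure can only be a rounded one, and the stated inputs do not round to it. Second, the sentence claims power for comparisons in general, while the effect behind it exists only on a scale that has a standard deviation. XI.1 lists the categorical tests first, and they include symptomatic PTSD and depression.

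A reader who takes the sentence at face value could treat a non-significant chi-square on PTSD status as strong evidence of no difference. The 0.5 SD calculation does not support that inference.

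**Working it through.** **Inputs.** Effect 0.5 SD, alpha 0.05, 134 per arm, 268 in total (XI.2); 1:1 allocation (VII.E.2). I take alpha as two-sided and also show one-sided.

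**1. The plan's own figure, continuous score.**

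Noncentrality = 0.5 × √(134/2) = 0.5 × 8.185 = 4.093.

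- Normal approximation, two-sided: Φ(4.093 − 1.960) = Φ(2.133) = 98.4%. One-sided: Φ(4.093 − 1.645) = Φ(2.448) = 99.3%.
- Noncentral t on 266 df (two-sided critical value 1.969): 98.3% two-sided, 99.3% one-sided.
- Wilcoxon with normal data (relative efficiency 3/π): about 97.9%; 97.8% by simulation.
- 150 per arm (all 300 enrolled): 99.1% two-sided, 99.6% one-sided.

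The stated 100% is therefore reproduced to within 2 points but not to the nearest percent at 134 per arm. A two-sided power of 99.5%, the least that rounds to 100%, needs 166 per arm at 0.5 SD, or about 0.56 SD at 134 per arm. Entering 268 as the per-arm number gives 99.99%, but XI.2 gives 268 as the total. How the 100% arose cannot be told from the document.

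**2. What 134 per arm does provide.**

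Detectable effect for 80% power = (1.960 + 0.842) × √(2/134) = 2.802 × 0.1222 = 0.342 SD (0.344 SD by noncentral t). For 0.5 SD, 64 per arm give 80% power and 86 per arm give 90%. The sample size is ample for the stated effect on a continuous score.

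**3. Whether the figure transfers to the categorical tests.**

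Power for a chi-square or logit comparison needs a comparator rate and an effect on the proportion or odds scale. XI.2 gives neither, so no power for these outcomes follows from it.

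**4. Illustration only.** The assumptions here are mine, not the protocol's: symptom status is a cut-off on a latent normal scale shifted by 0.5 SD, and the background rates in section 1.6 stand in for the Trauma Education arm.

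p2 = 1 − Φ(z(1−p1) + 0.5)

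Power = Φ[(|p1 − p2| − 1.960 × SE0) / SE1], where SE0 is the pooled and SE1 the unpooled standard error at 134 per arm.

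Worked case, p1 = 13%: z = 1.126, p2 = 1 − Φ(1.626) = 5.2%. Difference 0.0781, SE0 = 0.0351, SE1 = 0.0348. Power = Φ[(0.0781 − 0.0689)/0.0348] = Φ(0.265) = 60%.

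| Comparator rate | Shifted rate | Power |
|---|---|---|
| 13% | 5.2% | 60% |
| 19% | 8.4% | 71% |
| 29% | 14.6% | 82% |
| 32% | 16.7% | 84% |
| 60% (maximum over all rates) | 40% | 90% |

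A three-level outcome cut at tertiles, with the same shift and 2 df, has about 90%.

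**5. How far the illustration depends on its assumptions.**

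- Logistic latent scale (odds ratio 0.404): 54% to 87% over the same four rates, maximum 96%.
- Exact chi-square with continuity correction at 13%: 53%.
- If 0.5 is read as an arcsine effect size h: about 98%. But XI.2 says standard deviation, and h = 0.5 from 29% means a fall to 9.8%, equivalent to a latent shift of 0.74 SD.

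The categorical power therefore depends on both the rate and the effect chosen.

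**The case against.** The gap between 98% and 100% is immaterial: 1.7 points two-sided, 0.7 one-sided, and less with 150 per arm. It changes nothing in the design. That stands, and it keeps this a minor correction.

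The sentence before the power claim names a 0.5 SD effect, so the comparisons meant may simply be those on a scale with an SD. This is a fair reading, and the scope fault does rest on one unrestricted word. But nothing in XI.2 limits it, XI.1 puts categorical outcomes alongside the scores, and section 1.5 frames Phase 2 around a range of outcomes.

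A separate power calculation for each outcome type was not owed here and may sit in an analysis plan. That also stands: the point concerns what the sentence claims, not a missing calculation.

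The 60% to 84% figures are not the protocol's. Correct. The 19–32% range refers to 12 months while follow-up ends at 6 months, and the comparator arm receives an active booklet. A reader might infer from these figures that the trial is underpowered for PTSD or depression status, or that power for categorical outcomes is necessarily lower. The document supports neither. Both depend on treating the categorical effect as a dichotomised 0.5 SD shift, and a larger effect such as h = 0.5 would have about 98% power.

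**Conclusion.** The point holds as a minor correction. At 0.5 SD, two-sided alpha 0.05 and 134 per arm, t-test power is about 98% (99% one-sided), so 100% overstates it by under 2 points. The larger part of the fault is scope: the figure applies to continuous scores only and has no bearing on the chi-square and logit outcomes, whose power XI.2 leaves undetermined. The first conclusion uses only the protocol's inputs and the usual t-test assumptions. The second needs no assumption beyond XI.2 stating its effect solely in SD units. The binary power figures only show that the difference can be substantial under one plausible model; they do not measure this trial's power. The sample size of 268, raised to 300, is not in question.

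**What to change.** Replace the power sentence in XI.2 with wording such as:

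> 134 dyads per arm give about 98% power (two-sided alpha 0.05, t-test) to detect a 0.5 SD difference in a continuous score, and 80% power for about 0.34 SD; this figure does not apply to the categorical outcomes, for which power depends on the comparator rate and the assumed effect.

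If a power figure for a binary outcome is added, it should state its comparator rate and effect. The cost is one sentence in XI.2, with no change to the sample size, the tests or the outcomes.
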